6.2.1.4 Guidance for all other adverse reactions

Consider performing an analysis of serum potassium, calcium, phosphorus, and magnesium for all adverse reactions, if indicated. If electrolyte values are outside of the normal range, interrupt ribociclib administration, correct electrolytes with supplements or appropriate therapy as soon as possible, and repeat electrolyte testing until documented normalization of the electrolytes.

Patients who experience renal impairment (not due to other contributing factors) of grade 2 or higher during the treatment period should discontinue treatment and should be followed for safety assessments.

For patients taking bisphosphonates, the concomitant use of calcium is allowed for the treatment or prevention of hypocalcemia. Patients experiencing Grade 3/4 hypocalcemia should dose interrupt ribociclib until recovery to grade ≤ 1 and continue with the same dose level.

For all other adverse events please follow recommendations in [Table 6-6](#).

Table 6-6 Ribociclib dose adjustment and management recommendation for all other adverse reactions

Grade	Dose Adjustment and Management Recommendations
1	No dose adjustment recommended. Initiate appropriate medical therapy and monitor.
2	Dose interruption until recovery to grade ≤ 1 . Initiate appropriate medical therapy and monitor. Re-initiate ribociclib at the same dose. If the same toxicity recurs at grade 2, interrupt ribociclib until recovery to grade ≤ 1 . Re-initiate ribociclib at the next lower dose level.
3	Dose interruption until recovery to grade ≤ 1 . Initiate appropriate medical therapy and monitor. Re-initiate ribociclib at the next lower dose level. If toxicity recurs at grade 2: temporary dose interruption until recovery to grade ≤ 1 and reduce ribociclib dose the next lower dose level. If toxicity recurs at grade 3, discontinue ribociclib.
4	Discontinue ribociclib and treat with appropriate medical therapy.

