1.2.1.2.1 Clinical safety of ribociclib as single agent

As of 15-Jun-2015, 157 patients have been treated with single agent ribociclib in the first-in-human (FIH) phase I study; 85 patients have been treated in the initial dose escalation part for the 3 week on/1 week off regimen and 47 patients in the dose expansion part of the study; 18 patients were enrolled for the continuous dosing regimen with ribociclib and, 7 patients were enrolled in the liquid formulation cohort.

Patients with advanced solid tumors or lymphomas were treated with increasing doses of ribociclib orally, once daily (qd) for 21 days followed by a 1-week rest (28-day cycle). Doses ranging from 50 mg to 1200 mg were evaluated on this schedule. Treatment has been discontinued in 120 (90%) patients; the primary reasons for treatment discontinuation were: disease progression (106 [80%] patients); adverse events (AEs) (7 [5%] patients); death (2 [1.5%] patients); withdrawal of consent (3 [2%] patient); and loss to follow up (1 [1%] patient).

The most frequently reported AEs ($\geq 10\%$), regardless of grade, causality and ribociclib dose were: nausea (52.3%); fatigue (40.9%); diarrhea (37.1%); vomiting (35.6%); neutropenia (34.1%); anemia (32.6%); decreased appetite, thrombocytopenia (23.5% each); white blood cell count decrease (22.7%); leukopenia (22%); constipation (21.2%); dyspnea (20.5%); asthenia (19.7%); cough (18.2%); hyperglycemia (17.4%); headache, hypoalbuminemia (16.7% each); ECG QT prolonged (15.9%); abdominal pain, back pain, lymphocyte count decrease, pyrexia (15.2% each); AST increase, blood creatinine increased, dizziness, lymphopenia (14.4% each); peripheral edema (13.6%); neutrophil count decreased (12.9%); ALT increase, pain in extremity (12.1% each) and hypocalcemia (11.4%).

For either continuous or intermittent dosing, the onset of neutropenia (most frequently Grade 2) occurs by Day 15, reaching a nadir in the third or fourth week with recovery during the week of drug holiday for the three weeks on/one week off schedule. Some patients require additional time for recovery (7 to 14 days). QT changes become evident in the first cycle by Day 8 and later (once steady state is reached), are associated with the maximum drug levels between 1 to 8 h post-dose, and remain stable or improve in subsequent cycles.

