Table 1-5 Adverse events with suspected relationship to study treatment in study (CLEE011A2301)

Adverse events with suspected relationship to study treatment by preferred term and maximum grade (greater 5% in either arm) (Safety set)	Ribociclib + Letrozole n=334			Placebo + Letrozole n= 330		
Preferred Term	All grades (%)	Grade 3 n (%)	Grade 4 n (%)	All grades n (%)	Grade 3 n (%)	Grade 4 n (%)
Total	319 (95.5)	199 (59.6)	43 (12.9)	249 (75.5)	27 (8.2)	1 (0.3)
Neutropenia	199 (59.6)	130 (38.9)	29 (8.7)	13 (3.9)	2 (0.6)	0
Nausea	144 (43.1)	6 (1.8)	0	54 (16.4)	0	0
Alopecia	95 (28.4)	0	0	44 (13.3)	0	0
Fatigue	92 (27.5)	5 (1.5)	1 (0.3)	64 (19.4)	2 (0.6)	0
Diarrhea	72 (21.6)	3 (0.9)	0	39 (11.8)	0	0
Neutrophil count decreased	63 (18.9)	44 (13.2)	3 (0.9)	3 (0.9)	1 (0.3)	0
Vomiting	62 (18.9)	6 (1.8)	0	22 (6.7)	1 (0.3)	0
White blood cell count decreased	57 (17.1)	37 (1.1)	2 (0.6)	5 (1.5)	1 (0.3)	0
Hot flush	51 (15.3)	1 (0.3)	0	63 (19.1)	0	0
Arthralgia	48 (14.4)	1 (0.3)	0	52 (15.8)	1 (0.3)	0
Leukopenia	48 (14.4)	25 (7.5)	1 (0.3)	9 (2.7)	1 (0.3)	0
Anemia	46 (13.8)	2 (0.6)	0	9 (2.7)	3 (0.9)	0
Rash	45 (13.5)	2 (0.6)	0	10 (3.0)	0	0
Alanine aminotransferase increased	42 (12.6)	22 (6.6)	5 (1.5)	8 (2.4)	1 (0.3)	0
Constipation	40 (12.0)	0	0	20 (6.1)	0	0
Decreased appetite	39 (11.7)	3 (0.9)	0	18 (5.5)	0	0
Aspartate aminotransferase increased	36 (10.8)	12 (3.6)	2 (0.6)	8 (2.4)	3 (0.9)	0
Stomatitis	33 (9.9)	1 (0.3)	0	15 (4.5)	0	0
Pruritus	30 (9.0)	1 (0.3)	0	3 (0.9)	0	0
Asthenia	27 (8.1)	1 (0.3)	0	23 (7.0)	1 (0.3)	0
Headache	27 (8.1)	1 (0.3)	0	24 (7.3)	0	0
Dysgeusia	23 (6.9)	0	0	12 (3.6)	0	0
Dry mouth	21 (6.3)	1 (0.3)	0	14 (4.2)	0	0
Dizziness	19 (5.7)	0	0	21 (6.4)	0	0
Thrombocytopenia	19 (5.7)	1 (0.3)	0	0	0	0
Lymphocyte count decreased	18 (5.4)	12 (3.6)	0	3 (0.9)	2 (0.6)	0

The ongoing phase III study MONALEESA-3 (CLEE011F2301) investigates ribociclib in combination with the selective estrogen receptor degrader fulvestrant for the treatment of men and postmenopausal women with hormone receptor positive, HER2-negative, advanced breast cancer who have received no or only one line of prior endocrine treatment. Premenopausal patients are currently investigated in the ongoing phase III study MONALEESA-7 (CLEE011E2301), which is a randomized, double-blind, placebo-controlled

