6.2.1.1 Ribociclib

Recommendations for dose reduction, interruption or discontinuation of ribociclib in the management of study drug related adverse reactions are summarized in [Table 6-3](#), [Table 6-4](#), [Table 6-5](#) and [Table 6-6](#).

Clinical judgment of the treating physician should guide the management plan of each patient based on individual benefit/risk assessment. However, for events requiring a discontinuation in [Table 6-3](#), [Table 6-4](#), [Table 6-5](#) and [Table 6-6](#) or listed in Section 7.1, treatment must be discontinued.

If a patient inadvertently doses ribociclib on a rest day (e.g. days 22-28 of any given cycle), ribociclib should be interrupted to ensure 7 consecutive rest days and avoid overdose. The visit schedule will not be adjusted.

Table 6-3 Ribociclib dose adjustment and management recommendations for hematological adverse reactions

Toxicity/Grade	Dose Adjustment and Management Recommendations
Thrombocytopenia	
Grade 1($\geq 75 \times 10^9/L$)	No dose adjustment required.
Grade 2 ($\geq 50 \times 10^9/L - < 75 \times 10^9/L$)	Dose interruption until recovery to grade ≤ 1 . Re-initiate ribociclib at the same dose.
Grade 3 ($\geq 25 \times 10^9/L - < 50 \times 10^9/L$)	Dose interruption until recovery to grade ≤ 1 . Re-initiate ribociclib at the same dose level. If toxicity recurs at grade 3: temporary dose interruption until recovery to grade ≤ 1 and reduce ribociclib to the next lower dose level.
Grade 4($< 25 \times 10^9/L$)	Dose interruption until recovery to grade ≤ 1 . Re-initiate ribociclib at the next lower dose level. If toxicity recurs at grade 4: discontinue ribociclib
Absolute neutrophil count (ANC),	
Grade 1 ($\geq 1.5 \times 10^9/L$)	No dose adjustment required.
Grade 2 ($\geq 1.0 - < 1.5 \times 10^9/L$)	No dose adjustment required.

Toxicity/Grade	Dose Adjustment and Management Recommendations

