7.2.2.4 Laboratory evaluations

Laboratory evaluations should be performed locally at every protocol required visit ([Table 7-1](#)) or as frequently as clinically indicated.

The frequency of the assessments is indicated in [Table 7-1](#). All scheduled laboratory evaluations must be obtained \leq 7 days of the specified time periods, whether or not study treatment is administered. Screening examinations performed \leq 7 days of the first dose of study treatment do not need to be repeated on Day 1.

Laboratory values will not be documented in the eCRF unless clinically significant.

Any particular clinically significant findings present at screening at the time of informed consent must be documented in the Relevant Medical History/Current Medical Conditions eCRF. Abnormal laboratory parameters that induce clinical signs or symptoms, require therapy (e.g. hematologic abnormality that requires transfusion or hematological stem cell support), or require changes in study drug(s) constitute an adverse event (Section 8.1.2), must be recorded on the Adverse Event eCRF.

Laboratory certificates will be collected for this study.

Table 7-3 Local Clinical laboratory parameters collection plan

Test Category	Test Name
Hematology	White blood cell count (WBC) with differential (neutrophils, lymphocytes, monocytes, eosinophils, and basophils), hemoglobin (Hgb) and platelet count.
Biochemistry with fasting glucose	Sodium, potassium, calcium, corrected calcium, magnesium, total protein and albumin. AST (SGOT), ALT (SGPT), total bilirubin, direct bilirubin, GGT and alkaline phosphatase, and LDH. At Baseline and if clinically indicated: urea, creatinine, fasting glucose
Coagulation	At Baseline and if clinically indicated: INR
Fasting Lipid Panel	At Baseline and if clinically indicated: Total cholesterol, LDL-cholesterol, HDL-cholesterol and triglycerides

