7.2.2.4.2 Clinical chemistry

Serum chemistry tests are to be performed according to the Visit Schedules outlined in [Table 7-1](#). For details of the biochemistry panel refer to [Table 7-3](#).

Serum chemistry should be performed at screening, on treatment Day 1 (repeated prior to administration of the study drug, if greater than 7 days prior to Day 1), Cycle 1 Day 15, Cycle 2 Day 1 and Day 15 and Day 1 of each subsequent cycle and at End of treatment.

In the event of Grade 2, Grade 3 or Grade 4 non-hematological toxicities that require study drug dose modifications or interruptions, biochemistry tests should be repeated weekly until recovery to the baseline value or Grade 1.

Note: In the phase III study MonaLEEs-2 the majority (83.8%; 31/37) of the grade 3/4 ALT and AST increases with the combination therapy occurred during the first 6 months of treatment. The median time-to-onset of grade \geq 3 ALT/AST elevation was 57 days and 62 days, respectively (based upon medians of patients with events). The median time to resolution (to normalization or grade <3) (again based upon medians of patients with events) was 24 days in the ribociclib plus letrozole treatment group vs. 19 days for the placebo plus letrozole group.

In this study, laboratory values will be performed at the beginning of each cycle to assure that LFT abnormalities will be appropriately captured with this monitoring schedule.

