7.2.2.4.4 Urinalysis

Urinalysis is to be performed at Screening/Baseline according to local standard and as clinically indicated (dipstick analysis is sufficient).

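### Grade 2 or higher renal impairment calls for stopping treatment, but no scheduled on-treatment chemistry draw is required to include creatinine or any other renal marker

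*Protocol*

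**What the plan says.** The stopping rule is in Protocol Section 6.2.1.4: "Patients who experience renal impairment (not due to other contributing factors) of grade 2 or higher during the treatment period should discontinue treatment". It appears again under Renal Impairment in Section 6.2.1.4.1.

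Section 7.2.2.4.2 schedules serum chemistry at screening, Day 1 (if the last draw is more than 7 days old), Cycle 1 Day 15, and then "Cycle 2 Day 1 and Day 15 and Day 1 of each subsequent cycle and at End of treatment". It refers to Table 7-3 for the contents of the panel. Table 7-3 lists electrolytes, total protein, albumin, liver tests and LDH without restriction, then adds a separate line: "At Baseline and if clinically indicated: urea, creatinine, fasting glucose". The only reason given for testing every cycle is hepatic: "laboratory values will be performed at the beginning of each cycle to assure that LFT abnormalities will be appropriately captured".

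Section 7.2.2.4.4 treats urine the same way: "Urinalysis is to be performed at Screening/Baseline according to local standard and as clinically indicated".

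On how binding the rule is, Section 6.2.1.1 says: "Clinical judgment of the treating physician should guide the management plan of each patient based on individual benefit/risk assessment". It makes discontinuation mandatory for the events that require it in Tables 6-3 to 6-6 or that are listed in Section 7.1. The renal rule stands in the text outside those tables and is worded as a *should*.

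**The concern.** A rule that acts on a toxicity grade needs a measurement that yields the grade. The renal rule has none on a schedule. Grade 2 renal impairment may cause no symptoms, so nothing need prompt a test.

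Two things are at stake. A patient who meets the rule could stay on ribociclib unrecognised. The safety data also suffer: under Sections 8.1.1 and 8.1.2 a laboratory abnormality becomes an adverse event when it is clinically significant, causes symptoms, needs treatment or leads to a change in study treatment. A rise that nobody measures enters none of these routes, so reported renal events would reflect how often each site chose to test.

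The protocol gives reasons to look. Its single-agent data include "blood creatinine increased, dizziness, lymphopenia (14.4% each") among all-grade, all-cause events across doses, and Table 1-1 lists creatinine increase as a suspected serious event. Section 6.2.1.4.1 says the data do not support a dose recommendation in renal impairment. Inclusion criterion 11 requires creatinine below 1.5 mg/dL or clearance of at least 50 mL/min at entry, and no re-check is scheduled.

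**Working it through.** The plan gives no figure to reproduce. The check compares each rule with the measurement behind it, then counts draws.

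**Rules against measurements**

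| Rule | Scheduled on-treatment measurement |
|---|---|
| Haematological (Table 6-3) | Blood counts at C1D15, C2D1, C2D15, Day 1 of later cycles, end of treatment (7.2.2.4.1) |
| Hepatic (Table 6-4) | ALT, AST and bilirubin on the same days (Table 7-3, 7.2.2.4.2) |
| QTc (Table 6-5) | ECG at C1D15, C2D1, C2D15, Day 1 of cycles 3 to 6, end of treatment (Table 7-4) |
| Grade 3/4 hypocalcaemia (6.2.1.4) | Calcium in the routine panel (Table 7-3) |
| Grade 2 or higher renal impairment (6.2.1.4) | None |

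**Other possible routes to detection**

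- The Day 1 repeat precedes dosing, so it is still a baseline value.
- Weekly repeat biochemistry under 7.2.2.4.2 starts only after a toxicity that needs a dose change has been recognised.
- Routine potassium and other electrolytes may prompt a creatinine test, but they do not grade renal function.
- The liver follow-up list in 6.2.1.2 contains no creatinine.

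**Number of draws** (from 7.2.2.4.2, for a last-enrolled patient who completes the 80 weeks in Section 4.3)

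- Cycles: 80 / 4 = 20.
- C1D15, C2D1, C2D15: 3 draws.
- C3D1 to C20D1: 20 − 2 = 18 draws.
- Within cycles: 3 + 18 = 21. With end of treatment: 21 + 1 = 22.
- By C7D1 (6 cycles × 4 weeks = week 24): 3 + 5 = 8.
- Draws required to include creatinine, urea or another renal marker: 0 of 22.

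The end-of-treatment draw comes too late to trigger the rule but could still record an event. Table 7-1 is only partly readable in the text available, so the count rests on 7.2.2.4.2 and Table 7-3, which are intact.

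**How common might it be?** Table 1-5 (ribociclib plus letrozole, n = 334) is headed "Adverse events with suspected relationship to study treatment by preferred term and maximum grade (greater 5% in either arm"), and creatinine increase is not in it.

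- 17 / 334 = 5.09%, which would be listed.
- 16 / 334 = 4.79%, which would not.
- So at most 16 of 334 patients had a suspected creatinine increase of any grade. Scaled to this trial: 0.0479 × 500 ≈ 24.

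This bound covers one preferred term, events judged related, and any grade. It does not bound grade 2 or higher renal impairment recorded under other terms. Those patients were first-line with ECOG 0 or 1 (Section 1.2.6), whereas this trial admits ECOG 2 and pretreated patients, and that trial's creatinine schedule is not given.

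**The case against.** The strongest reply is that the tiering looks deliberate. Urea, creatinine, glucose, INR and lipids all sit in the baseline-or-indicated group. The on-treatment risks the protocol names as important are neutropenia, QT prolongation and hepatobiliary toxicity, and those are the ones monitored. Lipids also have a grade-based follow-up rule (7.2.2.4.3) without scheduled testing. The renal rule sits in guidance for all other reactions, where sites act on what they recognise, and it requires a judgment about other causes. This explains the design, but the protocol gives no reason for leaving creatinine out, and judgment still needs a value to work from. The lipid rule asks for repeat tests; the renal rule ends treatment.

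Several points limit the weight of the finding:

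- Creatinine may be tested at any visit when indicated, so the accurate statement is that no draw is *required* to include it.
- The 14.4% covers doses from 50 to 1200 mg in patients with solid tumours or lymphoma.
- Table 1-1 gives no count.
- Section 6.2.1.4.1 refers to the Investigator's Brochure, which cannot be checked here.

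The reply also says routine testing carries a cost. The renal rule is stricter than Table 6-6, which at grade 2 asks for interruption and restart at the same dose. More testing could therefore end treatment in some patients without symptoms. That is true, but it would be the protocol's own rule applied as written, with CTCAE 4.03 supplying the grades.

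Finally, enrollment was complete at Amendment 4, so an amendment may reach few patients or none. That narrows the remedy without removing the gap.

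**Conclusion.** The mismatch is real. The protocol says treatment should stop at grade 2 or higher renal impairment, yet none of the 22 scheduled draws over 80 weeks (8 by Cycle 7 Day 1) must include a renal marker. Recognition depends on each site's decision to test.

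The number of patients affected cannot be stated, and the closest source points to a low frequency. Renal toxicity is not a named important risk, and the gap does not touch the primary analysis of clinical benefit rate. It is a safety-monitoring and event-capture weakness that should be fixed because the repair is cheap. The conclusion assumes that Table 7-3 and Section 7.2.2.4.2 govern the panel and that no creatinine requirement is set elsewhere, such as in the Investigator's Brochure.

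**What to change.** In Table 7-3, move creatinine from the baseline-or-indicated line into the routine biochemistry list, so that it is reported at every scheduled chemistry visit for patients still on treatment. Leave the rule in 6.2.1.4 unchanged.

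The cost is one more analyte on blood already drawn, some mild rises to assess, and possibly a few discontinuations under the existing rule. The change needs a written amendment with ethics approval, and health authority approval where required (Section 12.1). It can reach only the treatment cycles that remain.

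If treatment has ended, no amendment is needed. State in the study report that on-treatment creatinine was not scheduled and that renal event counts therefore come from clinically prompted testing.

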6.2.1.4.1 Adjustment of starting dose in special populations

Renal Impairment

Insufficient data are available to provide a dosage recommendation for ribociclib in patients with renal impairment. A study in non-cancer patients with varying degrees of renal impairment and matched subjects with normal renal function is ongoing (CLEE011A2116). Refer to [Ribociclib Investigators Brochure] for more details. Based on rat ADME data, ribociclib was predominantly excreted in the bile as metabolites, with limited excretion of unchanged drug in urine.

Patients who experience renal impairment (not due to other contributing factors) of grade 2 or higher during the treatment period should discontinue treatment and should be followed for safety assessments.

Renal impairment does not affect letrozole PK in humans (Femara® Prescribing Information Novartis).

Studies with goserelin in female patients with renal impairment do not indicate a need for dose adjustment with the use of the depot formulation (Zoladex® Prescribing Information AstraZeneca).

Hepatic Impairment

A study in non-cancer patients with varying degrees of hepatic impairment (mild, moderate, severe based on Child-Pugh classification) and matched patients with normal hepatic function is ongoing ([CLEE011A2109]). Interim results indicated that the exposure (AUC and C_{max}) of ribociclib was similar between the mild hepatic impairment cohort and the normal cohort, was comparable in the moderate and severe cohorts, and both approximately 30% higher than in the normal cohort. In patients with severe hepatic impairment (Child-Pugh C), systemic exposure and terminal half-life of letrozole was twofold increased compared to healthy subjects. These patients should therefore be monitored closely.

Elderly

Insufficient data is available to provide a specific dosage recommendation in elderly population.

6.2.1.5 Letrozole

The established clinical dose of letrozole (2.5 mg/day) will be used and no dose modification of letrozole is planned in this study. The letrozole package insert should be consulted regarding full prescribing information and management of adverse events.

6.2.2 Anticipated risks and safety concerns of the study drug

Appropriate eligibility criteria as well as specific dose modification and stopping rules are included in this protocol. Recommended guidelines for prophylactic or supportive treatment for expected toxicities, including management of study-drug induced adverse events, e.g., neutropenia, liver toxicity and QT-prolongation are provided in Section 6.2.1. Refer to preclinical toxicity and or clinical data found in the Investigator's Brochure.

6.3 Concomitant medications

6.3.1 Permitted concomitant therapy

Medications required to treat AEs, manage cancer symptoms, concurrent diseases and supportive care agents, such as pain medications, anti-emetics and anti-diarrheal are allowed.

The patient must be told to notify the investigational site about any new medications he/she takes after the start of the study drug. All medications (other than study drug) and significant non-drug therapies (including physical therapy, herbal/natural medications and blood transfusions) administered 30 days before entering the study and during the study until safety follow up must be listed on the Concomitant Medications or the Procedures and Significant Non-Drug Therapies CRF.

